5.4.2 Schedule of Blood Sampling

The schedule of blood sampling is presented below in Table 2.

Table 2 Schedule of Blood Sampling

Parameter	Before Randomization	After Randomization but Before Initiation of Study CRRT ^a	During Study CRRTb	End of Study CRRT During Treatment Period ^c
Complete Blood Count (CBC) Blood Lactate Measurement	Screening			
pH Base Excess (ABG or VBG)		Baseline and Initiation	At 6, 12, 18, 24, 30, 36, 42, 48, 54, 60, 66, 72, 78, 84, 90, 96, 102, 108, 114, & 120 Hours ^b	When Study CRRT is Terminated
Serum Bicarbonate		Baseline and Initiation	At 6, 12, 18, 24, 30, 36, 42, 48, 54, 60, 66, 72, 78, 84, 90, 96, 102, 108, 114, & 120 Hours ^b	When Study CRRT is Terminated
Systemic iCa ²⁺		Baseline, 1 Hour Prior to Initiation of Study CRRT	At 1, 6, 12, 18, 24, 30, 36, 42, 48, 54, 60, 66, 72, 78, 84, 90, 96, 102, 108, 114, & 120 Hours ^b	When Study CRRT is Terminated
Post-Filter iCa ²⁺ (Prismocitrate 18 Arm Only)			At 1, 6, 12, 18, 24, 30, 36, 42, 48, 54, 60, 66, 72, 78, 84, 90, 96, 102, 108, 114, & 120 Hours ^b	When Study CRRT is Terminated
Serum Electrolytes: Sodium Potassium Chloride Phosphate Magnesium Anion Gap		Baseline and Initiation	At 6, 12, 18, 24, 30, 36, 42, 48, 54, 60, 66 72, 78, 84, 90, 96, 102, 108, 114, & 120 Hours ^b	When Study CRRT is Terminated
Creatinine BUN		Baseline and Initiation	Twice Daily	When Study CRRT is Terminated

Parameter	Before Randomization	After Randomization but Before Initiation of Study CRRT ^a	During Study CRRT ^b	End of Study CRRT During Treatment Period ^c
Bleeding Parameters: PT/INR PTT Hemoglobin Hematocrit Platelet Count	Screening	Baseline and Initiation	At Least Once Daily	When Study CRRT is Terminated
Blood Total Calcium Total Calcium/iCa ²⁺ Ratio	Screening	Baseline and Initiation	At 1, 6, 12, 18, 24, 30, 36, 42, 48, 54, 60, 66 72, 78, 84, 90, 96, 102, 108, 114, & 120 Hours ^b	When Study CRRT is Terminated
Liver Function Tests: Alanine Transaminase [ALT] Aspartate Transaminase [AST] Alkaline Phosphatase [ALP] Total Bilirubin	Screening	Baseline	As Determined by Local Standard-of-care	As Determined by Local Standard-of-care

ABG=arterial blood gases; ALT=alanine transaminase; AST=aspartate transaminase; ALP=alkaline phosphatase; CBC=complete blood count; CRRT=continuous renal replacement therapy; iCa^{2+} =ionized calcium; BUN=blood urea nitrogen, PT=prothrombin time; INR=international normalized ratio; PTT=partial thromboplastin time; VBG=venous blood gases

- ^a If patient has not been on standard-of-care CRRT, the Baseline and Initiation labs are the same. If patient has been on standard-of-care CRRT for < 24 hours the Baseline labs are those collected prior to the standard-of-care CRRT with exception of systemic iCa²⁺, which blood must be drawn 1 hour prior to initiation of Study CRRT. For Baseline Labs, the acceptable blood draw window is 24 hours. For Initiation Labs, the acceptable blood draw window is \pm 1 hour.
- ^b Acceptable blood draw window for serum bicarbonate, pH, systemic & post-filter iCa2⁺, blood total calcium, total calcium/ iCa²⁺ ratio and serum electrolytes (sodium, potassium, chloride, phosphate, magnesium, anion gap and base excess) is \pm 1 hour.
- ^c If a parameter has not been measured when study CRRT was terminated, the last available measurement collected during the treatment period will be used as the end of study measurement

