4.2 Inclusion Criteria

Each patient must meet the following inclusion criteria to be enrolled in this study.

- 1. Patient, or legally-authorized representative, has signed a written informed consent form (ICF).
- 2. Patient must be receiving medical care in an intensive care unit (ICU) [eg, medical ICU, surgical ICU, cardiothoracic ICU, Trauma ICU, Mixed ICU, other].
- 3. Patient age \geq 18 years.
- 4. Adult patients with AKI or other serious conditions who require treatment with CRRT.
- 5. Patients are expected to remain in the ICU and on CRRT for at least 72 hours after randomization.
- 6. Patients already receiving standard-of-care CRRT must be randomized within 24 hours of initiation of their standard-of-care CRRT.

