8.6 Safety Endpoints

Analysis of safety endpoints will be carried out on the FA Set based on the actual treatment groups for the following parameters:

- 1. A MMRM analysis will be used to evaluate differences between treatment groups in the change from baseline in serum bicarbonate and pH that are collected every 6 hours from the initiation of study CRRT during the 120 hour Treatment Period and at 120 hours or end of the Treatment Period. Frequencies and percentages will be provided for pH < 7.2 by time point and treatment group (thresholds indicative of metabolic acidosis).
- 2. A MMRM analysis will be used to evaluate differences between treatment groups in the change from baseline in blood total calcium concentrations that are assessed at 1 hour and every 6 hours from the initiation of study CRRT during the 120 hour Treatment Period and at 120 hours or end of the Treatment Period.
- 3. A MMRM analysis will be used to evaluate differences between treatment groups in the change from baseline in serum electrolytes (sodium, potassium, chloride, phosphate, and magnesium) that are collected every 6 hours from the initiation of study CRRT during the 120 hour Treatment Period and at 120 hours or end of the Treatment Period.

- 4. A descriptive summary of the total calcium/systemic iCa ratio as assessed at baseline, at initiation of study CRRT, 1 hour and every 6 hours from the initiation of study CRRT during the 120 hour Treatment Period and at 120 hours or end of the Treatment Period will be provided by treatment group. Frequencies and percentages will be provided for total calcium/systemic iCa ratio > 2.1 by time point and treatment group (threshold suggestive of citrate accumulation). Frequencies and percentages will be provided for anion gap > 11 mmol/L by time point and treatment group (threshold indicative of metabolic disturbance) as well as for base excess < -5 mmol/L.
- 5. A descriptive summary of the number, location, and duration of bleeding events along with the estimated blood loss during the 120 hour Treatment period will be provided by treatment group. The number and type of blood transfusion along with the number of units infused will also be summarized.
- 6. An analysis of covariance (ANCOVA) model will be used to evaluate differences between treatment groups in the change from baseline to final measurement in laboratory and vital signs measurements.

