5. STUDY DESIGN AND CONDUCT CONSIDERATIONS

5.1 Study Design

This study is a multi-center, prospective, non-blinded, one to one randomized study. A total of 160 adult patients, 80 in each study arm, will be enrolled at up to 15 investigational sites in the United States (US) and Canada. Patients meeting all of the inclusion criteria and none of the exclusion criteria of this protocol, and deemed treatable by either CRRT with Prismocitrate 18 solution or CRRT with no systemic anticoagulation, are eligible for enrollment in the study. If a patient is already receiving standard-of-care CRRT, they must be randomized within 24 hours of initiation of their standard-of-care CRRT. All patients will be treated with predilution CVVHDF as the study CRRT modality. Patients enrolled in the study will receive either Prismocitrate 18 anticoagulation or no systemic anticoagulation during their study CRRT, and extracorporeal circuit life will be monitored for up to 120 hours of study CRRT (treatment period). During the treatment period, the adequacy of anticoagulation in the Prismocitrate 18 patients will be assessed by monitoring extracorporeal circuit pressures and by assessment of systemic and post-filter blood iCa concentrations. Patients will be monitored for acid-base parameters and serum electrolytes at baseline prior to any CRRT), initiation (after randomization but before the initiation of study CRRT) and at pre-determined intervals during treatment. Information on bleeding events (number, location, duration) and the number and type of blood transfusions along with the number of units infused will also be collected.

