8.2 Handling of Missing Data

Missing data will neither be estimated nor replaced. No imputation of missing values will be performed. The survival type nature of data of the primary efficacy endpoint allows inclusion of any available information on extracorporeal circuit life in the statistical analysis according to the defined analysis populations.

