13.3 Secondary Analysis

A descriptive summary of systemic and post-filter blood iCa²⁺ concentrations as assessed at baseline (systemic only), 1 hour and every 6 hours during the 120 hours evaluation period and at 120 hours or end of the Evaluation period will be provided by treatment group. This summary will use the number of subjects n, mean, standard deviation, minimum, median and maximum. Changes from baseline will be analyzed by the number of subjects n, mean and standard deviation and t-test or Wilcoxon rank sum test, as applicable.

The individual blood iCa²⁺ concentrations will further be displayed graphically over time for each of the two treatment groups.

A MMRM analysis will be deployed to evaluate differences between treatment groups in blood i Ca^{2+} concentrations that are collected at baseline, 1 hour and every 6 hours during the 120 hours Evaluation period and at 120 hours or end of the Evaluation period from the initiation of CRRT. The model will include the illness severity score APACHE II, baseline i Ca^{2+} concentration, treatment group and time point as fixed effects, and an interaction between time point and treatment group will be included in the model only if treatment effects differ statistically significantly over time (p < 0.01).

In addition, frequencies and percentages will be provided for $iCa^{2+} < 1.1 \text{ mmol/L}$ by time point and treatment group (threshold indicative of decrease in iCa^{2+} despite adequate calcium compensation).

Daily delivered dose and overall delivered dose (both in mL/kg/hour) will be summarized using the number of subjects n, mean, standard deviation, minimum, median and maximum, as applicable. Treatment exposure will be analyzed carrying out the same descriptive summary for the percentages of the prescribed dose actually administered to the patient.

Effluent rate is considered an appropriate surrogate for the CRRT dose. Therefore, prescribed and delivered CRRT dose will be derived as follows based on the University of Alabama at Birmingham Continuous Venovenous Hemodiafiltration Protocol¹² used in the study:

$$Q_E = Q_{PBP} + Q_D + Q_{FR} + Q_R$$

where Q_E is the effluent rate (mL/hour),

Q_{PBP} is the pre-blood pump infusion rate which is the Prismocitrate 18 flow rate (mL/hour),

Q_D is the dialysate flow rate (mL/hour),

Q_{FR} is the patient fluid removal rate (mL/hour), and

Q_R is the post-filter replacement fluid rate (mL/hour).

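### The closing laboratory time point pools true 120-hour values with values from early stoppers, and the SAP's carry-forward footnote conflicts with its no-imputation rule

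*SAP*

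**What the plan says.** **Sampling.** SAP Table 2 (section 5.4.2) lists scheduled draws every 6 hours up to 120 hours, plus a 1-hour draw for the calcium measures. Footnote b allows ±1 hour for the metabolic parameters. A separate last column holds a sample "When Study CRRT is Terminated". Footnote c to that column says that if a parameter was not measured at that moment, "the last available measurement collected during the treatment period will be used as the end of study measurement". Protocol Appendix 1 has the same termination column but only footnotes a and b.

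**Analysis.** The SAP 13.3 summary of ionized calcium closes with a row "at 120 hours or end of the Evaluation period will be provided by treatment group". Besides the baseline and 1-hour values, the MMRM in the same section uses those taken "every 6 hours during the 120 hours Evaluation period and at 120 hours or end of the Evaluation period from the initiation of CRRT". Time point is a fixed effect, and a treatment-by-time interaction is added only if p < 0.01. SAP 14.3 applies the same analysis to bicarbonate, pH, total calcium and electrolytes, and adds threshold frequencies by time point. Protocol 8.5.2 uses the same closing time point. In protocol 8.6 the first MMRM covers "serum bicarbonate and pH that are collected every 6 hours from the initiation of study CRRT during the 120 hour Treatment Period", and that sentence continues with the same closing time point.

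**Missing data and changes.** SAP 8.2 states: "Missing data will neither be estimated nor replaced. No imputation of missing values will be performed". SAP 12 reports no departure from the protocol. SAP 8.5 sends additional blood draws into the MMRM without saying at which time level.

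**Length of treatment.** Under SAP 5.1, "extracorporeal circuit life will be monitored for up to 120 hours of study CRRT". Protocol 4.2 requires only that "Patients are expected to remain in the ICU and on CRRT for at least 72 hours after randomization".

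**The concern.** A level that carries the 120-hour label but holds values from any hour does not estimate the state of patients after 120 hours of study CRRT. Citrate supplies buffer, so its effects on bicarbonate, pH and calcium may change with exposure. The late rows are where a reader would look for alkalosis or citrate accumulation. Early stops (death, recovery, withdrawal, switch of therapy) are not random and may differ by arm.

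Footnote c is a second, separate problem. It is a last-observation-carried-forward rule in a plan that says no value will be replaced, and the plan does not say where the carried value is used. Two programmers following this text could produce different last rows.

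**Working it through.** **1. Does the closing time point mix hours?** Because 120 = 20 × 6, the six-hourly schedule already contains the 120-hour draw. The added end clause brings in something new only for a patient who stopped earlier. The termination column of Table 2 is the source of that value, and its hour is whatever hour CRRT stopped. No sentence in either document assigns the value to its actual hour or keeps it out of the closing level.

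**2. Can a value count twice?** Take a patient whose last draw is at 48 hours and who has no termination sample. The value stands at 48 hours and, under footnote c, is also the end-of-study value. If the end-of-study value feeds the closing MMRM level, one measurement supplies two of that patient's repeated measures. If it feeds only the final-measurement ANCOVA of SAP 14.4, it does not. The SAP does not say which.

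**3. Size with equal stopping in both arms.** The plan gives no figure to reproduce. It states no 120-hour difference, and the share discontinuing for reasons other than clotting is not shown in protocol 8.2 or SAP 5.2. What follows is illustration under assumptions.

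Let f be the share stopping before 120 hours, and m the mean of the arm difference at the stopping hour, as a fraction of the 120-hour difference. Then

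closing-level difference ÷ true 120-hour difference = (1 − f) + f × m.

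| Assumption | m | f = 30% | f = 50% | f = 70% |
|---|---|---|---|---|
| Linear growth, stops uniform over 0–120 h | 0.5 | 85% | 75% | 65% |
| Linear growth, stops uniform over 72–120 h | 96/120 = 0.8 | 94% | 90% | 86% |
| Plateau at 48 h, stops uniform over 0–120 h | (48 × 0.5 + 72)/120 = 0.8 | 94% | 90% | 86% |
| Plateau at 24 h, stops uniform over 0–120 h | (24 × 0.5 + 96)/120 = 0.9 | 97% | 95% | 93% |

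**4. Unequal stopping.** Suppose both arms follow the same linear path, so there is no true difference at any hour. With share q stopping at mean hour s, the closing-level mean is (1 − q) + q × s/120 of the 120-hour change.

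- 30% at 60 h gives 0.70 + 0.30 × 0.50 = 0.85. 50% at 48 h gives 0.50 + 0.50 × 0.40 = 0.70. Spurious difference: 15% of the 120-hour change.
- 30% at 72 h gives 0.70 + 0.30 × 0.60 = 0.88. 70% at 36 h gives 0.30 + 0.70 × 0.30 = 0.51. Spurious difference: 37%.
- Equal stopping gives 0.

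The documents do not settle whether stopping would differ by arm. Footnote e of SAP Table 1 and of protocol Appendix 2 has an unmitigated clotting or pressure alarm end the patient's treatment period. SAP 5.5.1 and protocol 6.7.1 have the circuit replaced. Those passages must be reconciled.

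**5. Where it would show.** There are 21 post-initiation time points for ionized calcium (1 hour plus 20 six-hourly). Without the interaction, the MMRM reports one overall arm effect and no 120-hour contrast. The mixing then shows mainly in the closing row of the summaries and threshold frequencies. A time-specific contrast is affected only if the interaction is fitted.

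**The case against.** The best defense is that footnote c defines an end-of-study measurement, a term SAP 13.3 does not use for the MMRM. Table 2 keeps the 120-hour draw and the termination draw in separate columns. The footnoted column also covers creatinine, urea nitrogen and bleeding parameters, which SAP 14.4 analyzes by ANCOVA on the final available value, and protocol 8.6 already plans a baseline-to-final comparison. On that reading footnote c serves the ANCOVA only, and the closing label merely echoes the collection wording of SAP 5.5.2 and 5.6. Much of this stands, and it rules out three stronger readings that a reader might infer:

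- *That carried-forward values are certain to enter the MMRM twice.* No passage says so. It is a possibility the text leaves open.
- *That the late arm difference is understated.* This needs growth with time and similar stopping in both arms. Protocol 5.2.3 has treatment adjusted to frequent laboratory results, so a plateau is plausible. It also links stopping the citrate infusion to the calcium ratio, so values at stopping could be extreme and not diluted. The 72-hour entry expectation makes very early stops less likely than a uniform pattern over 0–120 hours implies.
- *That SAP 12 is false.* Protocol 8.1 leaves analysis conventions to the SAP, so footnote c can be seen as elaboration. Listing it is a matter of transparency.

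The defense does not answer the closing label itself. SAP 13.3 uses it in the analysis text, with time point as a model effect, and nothing tells the programmer to split it. The conflict between footnote c and SAP 8.2 also remains on any reading.

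**Conclusion.** The point holds in limited form. As written, the closing level of the ionized calcium and safety laboratory analyses mixes early-stop values with 120-hour values. Separately, footnote c contradicts SAP 8.2 and has no stated use.

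The effect is confined to secondary and safety analyses. The primary circuit-life test is untouched, and the one secondary comparison in the testing hierarchy, percentage of prescribed dose delivered, does not use these values. The ANCOVA of SAP 14.4 openly targets the last value and is not in question.

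The size cannot be fixed from the documents. The 65% to 97% range rests on assumed stopping shares of 30% to 70%, assumed stopping times and an assumed shape of the effect over time. The direction is also open, since unequal stopping could create a difference where none exists. This warrants a correction to the wording before analysis and does not threaten the trial's main conclusion.

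**What to change.** Amend SAP 13.3 and 14.3, and align protocol 8.5.2 and 8.6:

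- Restrict the 120-hour level to draws within the plan's own ±1 hour window, that is 119 to 121 hours.
- Report end of treatment as a separate row, labelled as the last observed value.
- Enter termination samples in the MMRM at their actual draw time, under the same rule as additional draws in SAP 8.5. That rule has to be written, because SAP 8.5 gives none. It must say where an off-window draw goes: a 15-hour draw is equally far from 12 and 18 hours and outside both windows. If a scheduled and a termination draw fall at the same time point, keep the scheduled one.
- Limit footnote c to the final-measurement ANCOVA and the end-of-treatment row, state that exception in SAP 8.2, and list it in SAP 12.

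This needs wording and a visit-mapping rule but no new data. The price is fewer patients and a slightly wider interval at 120 hours.

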5.5 Efficacy Measures

5.5.1 Primary Efficacy Endpoint

The Prismaflex M150 Set extracorporeal circuit life will be assessed as a time-to-event endpoint over a maximum 120 hours by the duration of time for which each Prismaflex M150 Set can be used continuously over a maximum 72 hours period in each patient. The Prismaflex M150 Set will be replaced any time CRRT is stopped during the treatment period (regardless of duration) or any time a circuit is used for 72 continuous hours (i.e., "Advisory Time to Change Set"). The end of the extracorporeal circuit life will be defined by the occurrence of one or both of the following Prismaflex System alarms/conditions if the alarm cannot be mitigated. At this point, CRRT will be terminated and the extracorporeal circuit replaced:

- "Warning: Filter is Clotted" and/or
- "Advisory TMP Too High"

Note: The nurse at the clinical site will document the alarm and rationale to stop treatment on the eCRF. In addition, the Prismaflex logging information from the data cards (one card per patient) will be collected on an ongoing basis and anonymized data will be sent to Baxter for technical analysis. An Independent Adjudicator will make the final determination of the alarm cause by examining the applicable historical electronic data available surrounding the alarm events (for further details please see Section 9.9 Primary Endpoint Adjudication of study protocol).

The extracorporeal circuit life will be censored for cases where the Prismaflex M150 Set has been replaced for reasons other than reaching the end of the extracorporeal circuit life. Only filters for which the end of the extracorporeal circuit life was reached (i.e., one or both Prismaflex System alarms/conditions occurred as defined above and alarm causes have been confirmed by an Independent Adjudicator) will be considered 'events' in terms of the statistical analysis.

5.5.2 Secondary Efficacy Endpoints

Systemic and post-filter blood iCa concentrations will be assessed at baseline (systemic only), 1 hour and every 6 hours during the 120 hours Evaluation period and at 120 hours or end of the Evaluation period from the initiation of CRRT in each patient as indications of both the extent of calcium chelation prior to the CRRT filter and calcium restoration after the CRRT filter

Delivery of the prescribed CRRT dose will be based on daily recordings of both the effluent volume (in mL) and the patient's weight. These data will be used to calculate delivered dose (mL/kg/hour).

5.6 Safety Measures

- 1. Serum bicarbonate and pH will be measured at baseline and every 6 hours during the 120 hours Evaluation period and at 120 hours or end of the Evaluation period.
- 2. Blood total calcium concentrations will be measured at baseline, 1 hour and every 6 hours during the 120 hours evaluation period and at 120 hours or end of the Evaluation period from the initiation of CRRT.
- 3. Serum electrolytes (sodium, potassium, chloride, phosphate and, magnesium) will be measured at baseline and every 6 hours during the 120 hours evaluation period and at 120 hours or end of the evaluation period.
- 4. As indicators of citrate accumulation (along with pH), the total calcium/ iCa²⁺ ratio (both measurements in mmol/L) will be measured at baseline, 1 hour and every 6 hours during the 120 hours evaluation period and at 120 hours or end of evaluation period, anion gap and base excess will be measured at baseline and every 6 hours during the 120 hours evaluation period and at 120 hours or end of evaluation period.
- 5. The number, location and duration of bleeding events during the 120 hours Evaluation period will be collected. If a blood transfusion is needed during the 120 hours Evaluation period, the number and type of transfusions along with the number of units infused will be collected.
- 6. Change from baseline to final measurement in laboratory and vital signs measurements will be collected.
- 7. The incidence of adverse events (AEs) and serious adverse events (SAEs) from the time the patient signs the informed consent form (ICF) until the end of the study will be collected.

